7.1.2 Secondary Objectives

- To evaluate the PK of ivacaftor and metabolites M1 and M6 in subjects with CF who are <24 months of age at treatment initiation and have a *CFTR* gating mutation
- To evaluate the pharmacodynamics (PD) of ivacaftor treatment in subjects with CF who are <24 months of age at treatment initiation and have a *CFTR* gating mutation

[figure not shown]
7.2 Part A/B Cohort 8

For subjects 1 to <4 months of age, Parts A and B will be carried out sequentially in each individual subject, rather than performing a cohort analysis of Part A before starting Part B.

7.2.1 Primary Objectives

- To evaluate the safety of ivacaftor treatment in subjects with CF who are 1 to <4 months of age at treatment initiation and have an ivacaftor-responsive *CFTR* mutation (consistent with the approved mutations in the region)
- To evaluate the PK of ivacaftor and the ivacaftor metabolites M1 and M6 in subjects with CF who are 1 to <4 months of age at treatment initiation and have an ivacaftor-responsive *CFTR* mutation (consistent with the approved mutations in the region)

7.2.2 Secondary Objectives

- To evaluate the PD of ivacaftor treatment in subjects with CF who are 1 to <4 months of age at treatment initiation and have an ivacaftor-responsive *CFTR* mutation (consistent with the approved mutations in the region)
- 

8 STUDY ENDPOINTS

8.1 Part A

8.1.1 Primary Endpoints

- Safety, as determined by adverse events, clinical laboratory values (serum chemistry and hematology), standard 12-lead electrocardiograms (ECGs), vital signs, and ophthalmologic examinations (OEs)
- PK parameter estimates of ivacaftor and metabolites M1 and M6 after 4 days of ivacaftor treatment

[figure not shown]
8.2 Part B

8.2.1 Primary Endpoint

- Safety, as determined by adverse events, clinical laboratory values (serum chemistry and hematology), ECGs, vital signs, and OEs

8.2.2 Secondary Endpoints

- PK parameter estimates of ivacaftor and metabolites M1 and M6
- Absolute change from baseline in sweat chloride

[figure not shown]
8.3 Part A/B Cohort 8 Endpoints

[figure not shown]
8.3.1 Primary Endpoints

- Safety, as determined by adverse events, clinical laboratory values (serum chemistry and hematology), standard 12-lead ECGs, vital signs, and OEs
- PK parameter estimates of ivacaftor and the ivacaftor metabolites M1 and M6

8.3.2 Secondary Endpoints

- Absolute change from baseline in sweat chloride

9 STUDY DESIGN

9.1 Overview of Study Design

This is a Phase 3, 2-part, open-label study as depicted in [Figure 9-1](#). This study is designed to evaluate the safety, PK, PD, and efficacy of ivacaftor in subjects with CF who are <24 months of age at the time of treatment initiation (Day 1) and have an ivacaftor-responsive *CFTR* mutation on at least 1 allele. Part A is designed to evaluate the safety and PK of multiple-dose administration of ivacaftor in subjects <24 months of age over 4 days of dosing, and to confirm (or adjust if necessary) the doses for Part B. Part B is designed to evaluate the safety, PK, PD, and efficacy of ivacaftor in subjects <24 months of age over 24 weeks. Part A/B Cohort 8 is designed to evaluate the safety, PK, PD, and efficacy of ivacaftor in subjects with CF who are 1 to <4 months of age, ≥ 38 weeks gestation, weigh at least 3 kg at the time of treatment initiation (Day 1), and have an ivacaftor-responsive *CFTR* mutation (consistent with the approved mutations in the region) on at least 1 allele. Subjects will receive an initial low dose of ivacaftor (based on their Day 1 age and weight) up to Day 15, at which time the dose may be adjusted to better match the median adult exposure. Subjects are intended to remain on that dose until they are 4 months of age and at least 5 kg, after which the recommended age- and weight-appropriate dose(s) will be administered.

Part A:

Subjects will be enrolled in Part A sequentially in the following cohorts:

- **Cohort 1:** subjects aged 12 to <24 months
- **Cohort 2:** subjects aged 6 to <12 months
- **Cohort 3:** subjects aged 3 to <6 months

Enrollment in Part A will begin with subjects in Cohort 1. Enrollment for subjects in Cohort 2 will begin after an assessment of safety and PK data for subjects from Cohort 1. Enrollment for subjects in Cohort 3 will begin after an assessment of safety and PK data for subjects in Cohort 2.

PK data from each completed cohort in Part A will be used to update the population PK model and inform dose selection for the subsequent cohort before that cohort begins enrolling. If PK data from any cohort in Part A are insufficient to confirm the dose for that age group, additional subjects will be enrolled in the cohort until an appropriate dose is confirmed.

Part A of this study includes:

- Screening Period (Day -28 to Day -1)
- Treatment Period (Day 1 to Day 5):
 - 25-mg (for subjects 5 to <7 kg on Day 1), 50-mg (for subjects 7 to <14 kg on Day 1), or 75-mg (for subjects 14 to <25 kg on Day 1) ivacaftor will be administered every 12 hours (q12h) on Days 1 through 3 and 1 morning dose on Day 4. These doses may be amended at any time, based on available PK data from previous cohorts, and may result in additional doses or different weight strata. Data from each cohort in Part A will be used to update the population PK model and inform dose predictions for each subsequent (younger) cohort.
 - Study visits will occur on Days 1, 4, and 5.
 - PK samples will be collected before the morning dose on Day 4, between 2 and 4 hours, between 6 to 8 hours, and between 24 to 60 hours after the Day 4 dose.
 - For subjects who prematurely discontinue treatment, a PK blood sample will be collected at the Early Termination of Treatment (ETT) Visit (within 5 days after the last dose of study drug).
- Follow-up Telephone Call (Day 14)
- Follow-up OE (within 8 weeks \pm 14 days after the last dose of study drug, see Section 9.1.3.1).

Subjects who prematurely discontinue treatment before their last scheduled dose in Part A will be required to complete the ETT Visit, Follow-up Telephone Call, and Follow-up OE.

Part B:

Subjects will be enrolled in Part B sequentially in the following cohorts based on age at Day 1 of Part B:

- **Cohort 5:** subjects aged 12 to <24 months
- **Cohort 6:** subjects aged 6 to <12 months
- **Cohort 7:** subjects aged 4 to <6 months

Enrollment of subjects in Cohort 5 will begin following an assessment of:

- Safety and PK data from Part A for subjects from Cohort 1 and confirmation of dose for subjects aged 12 to <24 months.

Enrollment of subjects in Cohort 6 will begin after an assessment of:

- Safety and PK data from Part A for subjects from Cohort 2 and confirmation of dose for subjects aged 6 to <12 months.

- Safety data from Week 12 of Part B for at least 5 subjects in Cohort 5.

Enrollment of subjects in Cohort 7 will begin with enrollment of subjects aged 4 to <6 months following an assessment of:

- Safety and PK data from Part A for subjects from Cohort 3 and confirmation of dose in subjects aged 3 to <6 months.
- Safety data from Week 12 of Part B for at least 5 subjects in Cohort 6.

Subjects from Cohorts 2 and 3 who age out of the corresponding age cohort (Cohorts 6 or 7) at Part B Day 1 may enroll in an older age cohort in Part B with the Vertex medical monitor's permission. For example, subjects in Cohort 2 who will age out of Cohort 6 may enroll in Cohort 5; and subjects in Cohorts 3 or 4 who will age out of Cohort 7 may enroll in Cohort 6. Otherwise, subjects who will age out of the corresponding age cohort may enroll in the Extension Study.

Part B of this study includes:

- Screening Period (Day -28 to Day -1)
- Treatment Period (Day 1 to Week 24):
 - o Starting doses in Cohorts 5 and 6 of 25-mg (for subjects 5 to <7 kg on Day 1), 50-mg (for subjects 7 to <14 kg on Day 1), or 75-mg (for subjects 14 to <25 kg on Day 1) ivacaftor will be administered q12h for 24 weeks (or other suitable starting dose based on safety and PK data from Part A). At each study visit the ivacaftor dose for each subject will be reassessed based on body weight and adjusted if necessary.
 - o All subjects enrolled in Cohort 7 will receive a 25 mg dose of ivacaftor q12h until the subject reaches the age of 6 months. At each study visit after the age of 6 months, the ivacaftor dose for each subject will be reassessed based on body weight and adjusted, if necessary, as follows:
 - Subjects 5 to <7 kg will be dosed with 25 mg q12h
 - Subjects 7 to <14 kg will be dosed with 50 mg q12h
 - Subjects 14 to <25 kg will be dosed with 75 mg q12h
 - o Study visits will occur on Day 1 and Weeks 2, 4, 8, 12, 18, and 24.
 - o PK blood samples will be collected at the following time points:
 - Week 2: before the morning dose, between 2 and 4 hours and between 6 and 8 hours after the morning dose
 - Week 8: before the morning dose and 1 and 4 hours after the morning dose
 - Week 24: before the morning dose and between 2 and 4 hours after the morning dose
 - PK blood sampling at Week 24 is optional for subjects who undergo MBW (due to fasting requirements)
 - For subjects who prematurely discontinue treatment, a PK blood sample will be collected at the ETT Visit.

- o OEs will be performed at screening, Week 12, and Week 24.

[figure not shown]
All subjects who complete 24 weeks of study drug treatment will be eligible to enroll in the open-label treatment arm of an Extension Study. The Follow-up Visit will not be required for subjects who enroll in the treatment arm of this study.

Subjects who complete 24 weeks of study drug treatment who elect not to enroll in the treatment arm of the Extension Study will be required to complete the Follow-up Visit (4 weeks \pm 7 days after the last dose of study drug) and will be eligible to enroll in the observational arm of the Extension Study. The Follow-up Visit will not be required in the event that the subject initiates treatment with commercially available ivacaftor within 3 weeks of the Week 24 Visit.

Subjects who prematurely discontinue study drug treatment before their last scheduled dose will be required to complete the ETT Visit, Follow-up Visit, and Follow-up OE (see Section 9.1.3.1). The Follow-up Visit will not be required:

- If the ETT Visit occurs 3 weeks or later after the last dose of study drug.
- In the event that the subject initiates treatment with commercially available ivacaftor within 3 weeks of the ETT Visit.

Subjects who prematurely discontinue treatment will be eligible to enroll in the observational arm of the Extension Study. Subjects who are eligible will enroll in the Extension Study as soon as enrollment is open.

Figure 9-1 Schematic of Study Design

OE: ophthalmologic examination

^a Part A Follow-up OE will occur approximately 8 weeks after last dose of study drug.

^b All subjects who complete 24 weeks of study drug treatment will be eligible to enroll in the open-label treatment arm of the Extension Study. All other subjects will be eligible to enroll in the observational arm of the Extension Study. Subjects who prematurely discontinue will have the Part B Follow-up OE approximately 24 weeks after last dose of study drug.

Part A/B Cohort 8:

Subjects 1 to <4 months of age, ≥ 38 weeks gestation, and weighing at least 3 kg at the time of treatment initiation (Day 1) will receive an initial low dose of ivacaftor (5.7 mg q12h or 11.4 mg q12h based on their Day 1 age and weight) from Day 1 up to Day 15 (Figure 9-2). Subjects 3 months of age must weigh ≥ 5 kg on Day 1. This initial low dose is based on prior age- and weight-based simulations of exposure which accounts for potential variability in metabolic enzyme maturation affecting exposures. The initial dose is expected to result in exposures within or below the adult exposure range. On Day 4, PK samples from each subject will be collected before and after dosing and analyzed to determine the exposure and assess whether the initial dose needs to be adjusted to better match the median adult exposure.

A minimum of 6 and up to approximately 10 subjects will be enrolled, with at least 4 subjects evenly distributed in the age range 1 to <3 months, to have adequate data to assess the PK and safety in this age range.

Part A/B Cohort 8 of this study includes:

- Confirmed genotype; genotype testing is expected to be initiated prior to screening and results must be available prior to Day 1

- Screening Period (Day -28 to Day -14)
 - Due to limitations in the volume of blood that should be collected from the 1- to <4-month-old age group in a 28-day span, screening should be completed at least 14 days prior to Day 1 (treatment initiation)
- Initial Treatment Period (Day 1 up to Day 15):
 - Subjects will receive an initial low dose of ivacaftor (5.7 mg q12h or 11.4 mg q12h based on their Day 1 age and weight) from Day 1 up to Day 15, as follows:

Age	Weight Range	Starting Dose
1 month	≥3 kg	5.7 mg q12h
2 months	≥3 to <5 kg	5.7 mg q12h
2 months	≥5 kg	11.4 mg q12h
3 months	≥5 kg	11.4 mg q12h

[figure not shown]
All subjects must have gestational age ≥38 weeks and weigh ≥3 kg. Subjects 3 months of age must weigh ≥5 kg on Day 1.

- Study visits will occur on Days 1, 4, and 15.
- Follow-up Telephone Call (Day 1 evening)
- PK samples will be collected before the morning dose on Day 4, and between 2 to 4 hours and between 6 to 8 hours after the Day 4 morning dose.
- The Day 4 PK data will be reviewed by the study team to determine the dose to be administered on Day 15. The subject's Day 4 PK data will be used to calculate exposure to determine a dose that is expected to bring the exposure for the subject closest to the adult median. This potential dose adjustment will be communicated in writing to the principal investigator to administer to the subject on Day 15. If all PK samples collected on Day 4 are missing or cannot be analyzed, PK samples collected on Day 15 will be used to assess whether the initial dose should be adjusted at the Week 4 Visit.
- At the Day 15 Visit, a trough PK sample will be collected before the morning dose. The ivacaftor dose will be adjusted (based on the Day 4 PK data) if necessary, to either 5.7, 11.4, 17.1, 22.8, or 25 mg, and the adjusted dose will be administered q12h starting with the evening dose on Day 15.
- Subsequent Treatment Period (Day 16 to Week 24):
 - Follow-up Telephone Call (Day 17)
 - Study visits will occur on Weeks 4, 8, 12, 18, and 24.
 - The subject is intended to remain on the same dose from Day 15 until the subject is 4 months of age and at least 5 kg, after which the recommended age- and weight-appropriate dose(s) will be administered.
 - PK samples will be collected before the morning dose on Week 8, between 2 to 4 hours, and between 6 to 8 hours after the Week 8 morning dose.

- Additional PK samples will be collected before the morning dose on the Week 4, 12, 18, and 24 Visits to characterize the longitudinal PK profile.
- The entire treatment period of the study will be 24 weeks, after which subjects will be eligible to enroll in an Extension Study.
- Subjects who do not enroll in the Extension Study will have a Follow-up Visit within 4 weeks \pm 7 days after the last dose of study drug and a Follow-up OE within 12 weeks \pm 14 days after the last dose of study drug, (see Section 9.1.3.1).

Subjects who prematurely discontinue treatment before their last scheduled dose will be required to complete the ETT Visit, Follow-up Visit, and Follow-up OE. A PK blood sample will be collected at the ETT Visit (if the ETT Visit occurs within 3 days after the last dose of study drug).

Figure 9-2 Schematic of Part A/B Cohort 8 Study Design

OE: ophthalmologic examination

^a A Follow-up OE will occur approximately 12 weeks after last dose of study drug unless the subject enrolls in the Extension Study.

^b All subjects who complete 24 weeks of study drug treatment will be eligible to enroll in the open-label treatment arm of the Extension Study. All other subjects will be eligible to enroll in the observational arm of the Extension Study. Subjects who prematurely discontinue will have a Follow-up OE approximately 12 weeks after last dose of study drug.

9.1.1 Screening

Screening Visit assessments are listed in Part A [Table 3-1](#), Part B [Table 3-2](#), and Part A/B Cohort 8 ([Table 16-1](#)).

Screening will occur within 28 days before administration of study drug. Screening of subjects 1 to <4 months of age in Part A/B Cohort 8 should be completed at least 14 days prior to Day 1 (treatment initiation) to limit the volume of blood drawn in a 28-day span in this age group. The investigator (or an appropriate authorized designee at the study site) will obtain informed consent from the subject's parent or legal guardian.

To prepare for study participation, the subject's parent or legal guardian will be instructed on the study restrictions (Section [10.3](#)).

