Adverse events	Continuous from signing ICF through the ETT (if required) and Follow-up Visit (see Section 14.1.1.3)		Ocular adverse events only
Medications and procedures review	Continuous from 28 days before the Screening Visit through the ETT and Follow-up Visit (if required; see Section 10.3.1)		

ECG: electrocardiogram; ETT: Early Termination of Treatment; ICF: informed consent form; OE: ophthalmologic examination; PK: pharmacokinetic.

Table 3-4 Study VX15-770-124: Part A/B Cohort 8 (Screening, Treatment, Early Termination of Treatment, and Follow-up Periods)

Event/Assessment	Screening Period	Treatment Period (Day 1 to Week 24)							Early Termination of Treatment Visit ^a	Follow-up Visit ^b	Follow-up Ophthalmologic Examination ^c
	Day -28 to Day -14	Day 1	Day 4	Day 15 (± 1 Day)	Day 17 (± 1 Day)	Week 4 (± 5 Days)	Week 8 (± 5 Days)	Weeks 12, 18, and 24 (± 5 Days)	As Soon as Possible After the Last Dose of Study Drug	4 Weeks (± 7 Days) After Last Dose of Study Drug	12 Weeks (± 14 Days) After Last Dose of Study Drug
Informed consent ^d	X										
Inclusion/exclusion criteria review	X	X									
Clinic visit/ Assessment contact	X	X	X	X		X	X	X	X	X	
Telephone contact		pm			X						
Demographics	X										
Medical history	X										
██████████ weight ^e	X	X	X	X		X	X	X	X	X	
Physical examination ^f	X	X	X	X		X	X	X	X	X	
Vital signs ^g	X	X	X	X		X	X	X	X	X	
12-lead ECGs ^h	X		X			X		X	X		
Ophthalmologic examinations ⁱ	X							X ^j	X		X
Serum chemistry ^k	X	X	X	X		X	X	X	X	X	
Hematology ^k	X			X		X		X	X	X	
PK blood collection ^l			X ^m	X		X	X ^l	X	X ⁿ		
Sweat chloride test ^o	X	X		X		X	X	X	X		
Study drug administration ^q		X	X	X		X	X	X			

-
- ^a Subjects who prematurely discontinue treatment before their last scheduled dose will be required to complete the ETT Visit as soon as possible after the last dose of study drug and the Follow-up Visit. All subjects who prematurely discontinue from study drug treatment in Part A/B Cohort 8 will be eligible to enroll in an observational arm of the Extension Study.
- ^b The Follow-up Visit is not required if the subject completes the Part A/B Cohort 8 treatment period and enrolls in the treatment arm of the Extension Study. For all other subjects, the Follow-up Visit is not required if the ETT Visit occurs 3 weeks or later after the last dose of study drug (ivacaftor) or in the event that the subject initiates treatment with commercially available ivacaftor within 3 weeks of the final scheduled treatment visit or ETT Visit.

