- ^c Subjects who prematurely discontinue ivacaftor treatment in Part A/B Cohort 8 and received at least 1 dose of ivacaftor treatment in Part A/B Cohort 8 will have a Follow-up OE 12 weeks after the last dose of study drug. Subjects enrolling into the Extension Study within 12 weeks after the last dose of study drug are not required to have the Follow-up OE (the OE will be performed in the Extension Study instead). Subjects who initiate treatment with commercially available ivacaftor within 3 weeks of the ETT Visit will not have the Follow-up OE.
- ^d Informed consent may be obtained before the Screening Visit and must be obtained before any screening assessment is performed.
- ^e [REDACTED] weight must be measured with the subject in a dry diaper or dry underclothes only (see Section 12.5.1 for details). [REDACTED] weight measurements will be made before the morning dose on Day 1.
- ^f Full physical examinations will occur at the Screening, Week 24, and Early Termination of Treatment (ETT) Visits; abbreviated physical examinations will occur at all other study visits.
- ^g Vital signs include blood pressure (systolic and diastolic), temperature, heart rate, respiration rate, and pulse oximetry. The subject should rest for at least 5 minutes, if possible, before having vital signs measured. Day 1 vital sign measurements will be collected before the morning dose. Temperature must be obtained by the same method throughout the study.
- ^h All 12-lead ECGs will be performed before the morning dose. The subject should rest for at least 5 minutes, if possible, before having the ECG performed. The ECG will be performed before any other procedures that may affect heart rate, such as blood draws.
- ⁱ The screening OE may be performed at any time from screening until before the first dose on Day 1. If an adequate slit-lamp examination cannot be conducted at screening, subjects will not be enrolled until an adequate repeat slit-lamp examination is completed (within 4 weeks of the Screening Period). Eligibility criteria regarding the ophthalmologic findings must be met prior to dosing.
- ^j OE to be performed at the Week 12 and Week 24 Visits.

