#### 8 STATISTICAL ANALYSIS

#### 8.1 General Considerations

The Schedule of Assessments is provided in Appendix A. The precision standards for reporting safety and efficacy variables are provided in an internal Biometrics document that specifies the programming rules including the precision for derived variables.

All individual subject data for subjects who were eligible for study enrollment or received at least 1 dose of study drug will be presented in individual subject data listings.

Continuous variables will be summarized using the following descriptive summary statistics: the number of subjects (n), mean, standard deviation (SD), standard error (SE), median, minimum value (min), and maximum value (max), and 95% confidence intervals [CI], as appropriate.

Categorical variables will be summarized using counts, percentages, and 95% CI (as appropriate).

**Baseline value**, unless specified otherwise, will be defined separately for Parts A, and combined Part B and Part A/B Cohort 8 as the most recent non-missing measurement (scheduled or unscheduled) collected before the first dose of study drug in the respective study part.

Change (absolute change) from baseline will be calculated as Postbaseline value – Baseline value.

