#### 8.4.3 Electrocardiogram

For treatment-emergent ECG measurements, a summary of raw values and change from baseline values will be provided by visit. In addition, the number and percentage of subjects by maximum on-treatment value and by maximum on-treatment increase from baseline in QTc intervals will be presented. A listing of abnormal ECG complexes from the ambulatory recordings will be presented.

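### Cohort 8's only scheduled pre-treatment ECG falls at Day -28 to Day -14 for a blood-volume reason that does not apply to an ECG, so the Day 4 and Week 4 changes from baseline span mostly or substantially untreated time

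*Protocol*

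**What the plan says.** Protocol Table 3-4 sets the Cohort 8 screening period at "Day -28 to Day -14". Section 9.1.1 gives the reason: screening "should be completed at least 14 days prior to Day 1 (treatment initiation) to limit the volume of blood drawn in a 28-day span". ECGs are scheduled at screening, Day 4, Week 4, Weeks 12, 18 and 24, and early termination. The Day 1 cell is empty, and the Cohort 8 schedule in SAP Appendix A is the same. Footnote h adds only that "All 12-lead ECGs will be performed before the morning dose".

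Other assessments that need no blood are treated differently in the same table. Footnote i says of the eye examination: "The screening OE may be performed at any time from screening until before the first dose on Day 1". Footnote g says: "Day 1 vital sign measurements will be collected before the morning dose". Weight and sweat chloride are also measured on Day 1.

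SAP Section 8.1 defines baseline as "the most recent non-missing measurement (scheduled or unscheduled) collected before the first dose of study drug". SAP Section 8.4.3 summarises raw ECG values and changes by visit, and the number and percentage of subjects by maximum on-treatment QTc. It also states that results by "maximum on-treatment increase from baseline in QTc intervals will be presented". ECG is a component of the Cohort 8 primary safety endpoint (Protocol Section 8.3.1).

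**The concern.** A change from baseline is easiest to read when the baseline immediately precedes treatment. Here the baseline trace is at least two weeks old at the first dose, in infants aged 1 to under 4 months, and there is no control group. Any untreated change over those weeks enters the reported change.

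This matters most at Day 4, the first on-treatment ECG and the only scheduled one before the Day 15 dose adjustment. Protocol Section 9.3.1 lists ECGs among the data weighed in dosing decisions, and Section 12.6.4 has the investigator compare ECG findings with baseline. The longest gap relative to treatment time therefore falls on the earliest comparison.

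The SAP also presents safety tables by cohort and overall for Part B and Cohort 8 combined. Part B screening may run to Day -1, whereas Cohort 8 screening should stop by Day -14, so the overall column mixes baselines collected under different rules.

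**Working it through.** **1. The stated reason.** Protocol Table 12-1 gives Cohort 8 blood volumes by visit. Their sum, excluding early termination, is 2.3 + 2.2 + 2.6 + 2.8 + 2.8 + 2.6 + 11.7 = 27.0 mL, which reproduces the total stated in Section 12.3.1. For a 3 kg infant that section assumes 240 mL of blood and expects no more than about 3% to be drawn in any 4 weeks: 0.03 × 240 = 7.2 mL. Screening, Day 1 and Day 4 together take 2.3 + 2.2 + 2.6 = 7.1 mL. The blood constraint is therefore real. An ECG adds 0 mL, so the constraint gives no reason to move it.

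**2. Untreated share of each interval.** There is no Day 0, so the time from Day -k to Day d is k + d - 1 days. Of this, k days precede treatment, and the untreated share is k / (k + d - 1). The table uses k = 14 and k = 28 and the SAP Appendix D target days.

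| Visit (target day) | k = 14 | k = 28 | Interval with a Day 1 baseline |
|---|---|---|---|
| Day 4 (4) | 14/17 = 82% | 28/31 = 90% | 3 days |
| Week 4 (28) | 14/41 = 34% | 28/55 = 51% | 27 days |
| Week 12 (84) | 14/97 = 14% | 28/111 = 25% | 83 days |
| Week 18 (126) | 14/139 = 10% | 28/153 = 18% | 125 days |
| Week 24 (168) | 14/181 = 8% | 28/195 = 14% | 167 days |

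With a Day 1 pre-dose baseline the untreated share is 0 at every visit.

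**3. Window extensions.** Section 9.1.1.3 allows 2 more weeks, or 4 if a slit-lamp examination is repeated. The gap could then reach 28 + 14 = 42 or 28 + 28 = 56 days, and the Day 4 share 42/45 = 93% or 56/59 = 95%. These limits cannot apply in full to an infant dosed at 1 month (about 30.4 days old).

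**4. Age at baseline ECG (nominal window).** Age on Day 1 minus 28 and minus 14 days, taking a month as 30.4 days:

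- dosed at exactly 1 month: 2.4 to 16.4 days
- dosed at 2 months: about 33 to 47 days
- dosed at 3 months: about 63 to 77 days

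**5. Comparison with Part B.** Part B also has no Day 1 ECG, and its window also opens at Day -28, so the longest nominal gap is the same. The shortest is not. At Week 4, Part B's first on-treatment ECG, the untreated share can be as low as 1/28 = 3.6% in Part B but no lower than 34% in Cohort 8.

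**The case against.** Several points on the other side stand.

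- **Single-arm design.** A reader might infer that the early ECG is what confounds every Cohort 8 change with development, and that moving it would cure this. The documents do not support that. Twenty-four weeks of uncontrolled follow-up do most of the confounding at later visits: a Day 1 baseline shortens the Week 24 interval only from 181-195 days to 167.
- **No rate of change.** A reader might want to put the bias in milliseconds. Neither document gives a rate or direction of QTc change in infants, so only the interval in days can be computed. That some untreated change occurs is itself an assumption.
- **Unscheduled traces.** The early ECG is the only scheduled pre-treatment trace, not the only possible one. Section 12.6.4 provides for extra ECGs when clinically indicated, and the SAP rule would take a later pre-treatment trace as baseline.
- **Safeguards.** Raw values and maximum on-treatment QTc do not use baseline. All traces are evaluated centrally by a pediatric cardiologist, and clinically significant abnormalities become adverse events. The analysis is descriptive, in 6 to about 10 infants.
- **Lead time.** No eligibility criterion names the ECG, but exclusion criterion 1 rests on investigator judgement, and an early trace leaves time for review before dosing. It would be wrong to say that an early ECG serves no purpose.
- **Extreme ages.** A baseline at about 2 days of age requires dosing at exactly 1 month and screening on the first permitted day, after consent. It is the extreme of the range, not the typical case.

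None of this explains why the eye examination may run up to the first dose and vital signs are repeated on Day 1 while the ECG is not.

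**Conclusion.** The point holds for the early visits. Under the planned schedule, with no unscheduled pre-treatment ECG, every Cohort 8 ECG change contains 14 to 28 untreated days, and more if the window is extended. These are most of the Day 4 interval (82-90%) and a third to a half of the Week 4 interval (34-51%). They are a minor part by Week 24 (8-14%), where the single-arm design is the main limitation. Maximum QTc increase carries the same gap, whichever visit supplies the maximum.

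The shares rest on nominal visit days and the nominal screening window. The size and direction of any resulting bias are unknown. The early ECG does not invalidate the ECG safety data, because the baseline-free summaries stand. It is an avoidable weakness in one component of the primary safety endpoint.

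**What to change.** **Schedule.** In Protocol Table 3-4 and the Cohort 8 schedule in SAP Appendix A, add a pre-dose ECG on Day 1. Alternatively, allow the screening ECG up to the first dose, as footnote i does for the eye examination. Adding the Day 1 trace is firmer, because permission alone does not guarantee a short gap. In either case the existing SAP baseline rule picks up the later trace without rewording. The cost is one extra non-invasive ECG if the early trace is kept for review before dosing, none if it is moved, and no blood. Day 1 is already a clinic visit with pre-dose vital signs.

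**Reporting.** SAP Section 9.1 describes in the past tense an analysis made after all Cohort 8 subjects had completed participation, so the schedule change probably comes too late for these infants. For them:

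- list the days from baseline ECG to Day 1 and the age at baseline ECG for each infant
- present the Day 4 and Week 4 ECG changes beside the raw values, with a note that the change includes this untreated period

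This needs two derived variables and a footnote. SAP Section 3 provides for changes made after database lock to be documented in the clinical study report.
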